8.3. Trial Procedures

The following trial procedures will be developed and documented separately:

- Referral screening guidelines
- Data collection guidelines
- Verification and adjudication of outcome data collection
- Long-term follow-up: either at entry to the trial or during the follow-up period, we will invite parents and young people (aged 16-17 years) to additionally consent to long-term follow-up using routinely collected data through linkage with centrally held NHS and educational records.

8.4. Withdrawal Procedures

Participants are free to withdraw from the trial at any time and for any reason.

Where the parent/carer has consented in their own right and on behalf of the child/young person (<16 years) both parties will cease their involvement in the trial should the parent/carer withdraw this consent.

Where young people aged 16 or 17 have consented for their own involvement they can continue to participate in the trial in the event of the parent/carer's withdrawal, however, the parent/carer involvement would not continue should the young person withdraw consent.

Participants may withdraw from the intervention, follow-up questionnaires and / or data collection from records in any of the following combinations:

- Withdraw from trial intervention but continue to complete follow-up questionnaires in accordance with the trial schedule and continue to permit trial data collection from records for use in the analysis.
- Withdraw from trial intervention and follow-up questionnaires but continue to permit trial data collection from records for use in the analysis.
- Withdraw from the trial intervention and follow-up questionnaires and withdraw consent for any further data collection from records.
- Following completion of the trial intervention, withdraw consent for follow-up questionnaires but continue to permit trial data collection from records for use in the analysis.
- Following completion of the trial intervention, withdraw consent for follow-up questionnaires and withdraw consent for any further data collection from records.
- Following completion of the trial intervention and follow-up questionnaires, withdraw consent for any further data collection from records.

Trial name:	STADIA	Protocol version:	4.1	Date:	01-Aug-2022	Page:	39 of 73	
Written using WPD	/ritten using WPD 3.1 version 2.0 30-Oct-2017. Effective date: 30-Nov-2017. Template Author: [name]							

Withdrawn participants will not be replaced. Data collected prior to withdrawal will be retained and used in the analysis.

9. Adverse Event Reporting

The risks of the trial are comparable to that of usual practice. The trial intervention (completion of the DAWBA) is conceptually similar to what might be done as part of usual practice (i.e., children/parents referred to CAMHS may already be sent questionnaires about their difficulties before the referral is accepted). Furthermore, the DAWBA is widely used in research for data collection/outcome measurement therefore, although utilised as an intervention in the STADIA trial, the risks may be regarded as similar to those of an observational/questionnaire study.

The only adverse outcomes that might be plausibly related to the trial procedures are worry or distress for the child/young person and/or parent/carer as a result of the sensitive nature of some questions and increased focus on existing difficulties. However, the trial participants are children and young people referred to CAMHS because of emotional difficulties and symptoms of depression and/or anxiety are likely to be prevalent, therefore these are expected outcomes. Such difficulties may also be observed in the parents/carers of children referred to CAMHS. Measures of depression in both young people and parents/carers are already collected in the trial and will capture any potential deterioration which may be indicative of adverse effects. Data to inform safety oversight will therefore be collected during routine follow-up, from existing outcome measures.

The pre-defined safety outcomes will be:

- Symptoms of depression in child/young people: A significant worsening of symptoms of depression in children/young people, defined as a score indicative of depression (27 or above) on the Mood and Feelings Questionnaire (MFQ) completed at follow-up, where this represents a deterioration from baseline of 5 points or more.
- Parental depression: A significant worsening of parental depression, defined as a score indicative of depression (15 or above) on the Patient Health Questionnaire (PHQ-9) completed at followup, where this represents a deterioration from baseline of 5 points or more.
- Self-harm: Frequency of self-harm in children/young people (aged 11+) based on self-report questionnaire completed at 6- and 12-months post-randomisation.
- Hospital admissions: the number of children/young people admitted to hospital (either physical or mental health-related) due to emotional difficulties as reported in the resource use questionnaire completed at 6- and 12 months post-randomisation.
- A&E attendances: the number of children/young people attending A&E (either physical or mental health-related) due to emotional difficulties as reported in the resource use questionnaire completed at 6- and 12 months post-randomisation.
- Deaths: the number of deaths of children/young people between baseline and 12 and 18 month follow-up.

The number of participants meeting these criteria will be reported on an ongoing basis to the TMG and TSC. Data will be presented by arms to the DMC.

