8.1. Summary of assessments

The summary of assessment is detailed in Table 5.

Trial name:	STADIA	Protocol version:	4.1	Date:	01-Aug-2022	Page:	34 of 73
Written using WPD	Written using WPD 3.1 version 2.0 30-Oct-2017. Effective date: 30-Nov-2017. Template Author: [name]						

Table 5. Summary of assessments

Time-point	Maxim	um 10 working	days from ref	6 months post- randomisation	12 months post- randomisation	18 months post- randomisation		
Activity	Screening and invitation	Eligibility and enrolment	Consent and baseline			Follo	w-Up	
Initial eligibility screen of referral information	Х							
Telephone invitation to participate	Х							
Verbal agreement to participate		X						
Confirm eligibility		X						
Obtain enrolment data		X						
Participant enrolment		Х						
Written informed consent/assent (online)			Х		Intervention			
Baseline demographics (parent/carer and young person aged 16 & 17)			Х		DAWBA in			
MFQ (parent/carer and child/young person aged 11+)			х	sation	addition to usual	Х	Х	
RCADS (parent/carer and child/young person aged 11+)			х	Randomisation	practice	Х	Х	
SDQ (parent/carer and child/young person aged 11+)**			Х	Ran	Or	х	Х	
Self-harm measure (child/young person aged 11+ only)			Х		Usual practice only	х	х	
PHQ-9 (parent/carer only)			Х	-		Х	Х	
GAD-7 (parent/carer only)			х	-		Х	Х	
CHU9D (child/young person self-report if aged 11+ or parent/carer proxy if child aged <11 or 11-			х			x	Х	
15 and not self-reporting)								
EQ5DY (child/young person self-report if aged 11+ or parent/carer proxy if child aged <11 or 11- 15 and not self-reporting)			х			x	х	
EQ5D5L (parent/carer only)			Х	1		Х	Х	
Trial name: STADIA Protocol version: 4.1	Date: 01-A	ug-2022 Pa	ge: 35 of 7	3	1	1		1

Resource Use Questionnaire (parent/carer and young person aged 16 & 17)		x		х	х	
CRIES-8 (child/young person self-report if aged						
11+ or parent/carer proxy if child aged <11 or 11-		X		X	Х	
15 and not self-reporting)						
Data collection from records***		X		Х	Х	Х
* For sites where the waiting time for the CAMHS accepta	nce decision usuall	y exceeds 10 workir	ng days from refe	rral receipt, recruitme	nt activities may	
start and/or continue beyond 10 working days from refer	ral receipt, providin	g the intervention p	period can be con	pleted prior to the CA	MHS referral	
decision.						
**For participants in the intervention arm, the baseline S	DQ will be collected	l as part of the DAW	/BA, completed p	ost-randomisation.		

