9.1. Reporting Requirements

9.2. Adverse Events

Relevant adverse events (AEs) are outcomes (e.g. symptoms of depression and anxiety) and will be collected during routine follow-up using participant questionnaires. Separate AE reporting will not be required.

Trial name:	STADIA	Protocol version:	4.1	Date:	01-Aug-2022	Page:	40 of 73	
Written using WPD	Nritten using WPD 3.1 version 2.0 30-Oct-2017. Effective date: 30-Nov-2017. Template Author: [name]							

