9.7. Data Monitoring Committee

The independent Data Monitoring Committee (DMC) will review all safety data.

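### Worry or distress is the only harm the protocol thinks plausible, yet none of its six pre-defined safety outcomes measures anxiety, although RCADS and GAD-7 are already collected

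*Protocol*

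**What the plan says.** Section 9 of the protocol sets out the safety rationale. It states the expected harm: "The only adverse outcomes that might be plausibly related to the trial procedures are worry or distress for the child/young person and/or parent/carer". It notes that symptoms of depression and/or anxiety are likely to be common in this population, and then says how worsening will be picked up: "Measures of depression in both young people and parents/carers are already collected in the trial and will capture any potential deterioration".

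Six safety outcomes follow, repeated in the safety rows of Table 6: MFQ worsening in the child, PHQ-9 worsening in the parent, self-harm (age 11 and over), hospital admissions, A&E attendances, and deaths. On reporting, section 9 says: "The number of participants meeting these criteria will be reported on an ongoing basis to the TMG and TSC", and then: "Data will be presented by arms to the DMC". Section 9.7 adds: "The independent Data Monitoring Committee (DMC) will review all safety data".

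Section 9.2 reads: "Relevant adverse events (AEs) are outcomes (e.g. symptoms of depression and anxiety) and will be collected during routine follow-up using participant questionnaires". On that basis it requires no separate AE reporting.

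Table 5 and section 8.2 schedule RCADS (parent and young person aged 11+) and GAD-7 (parent) at baseline, 6 and 12 months, the same schedule as MFQ and PHQ-9. In Table 6 both anxiety scales appear only as secondary outcomes, analysed as a mean difference adjusted for baseline.

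**The concern.** Section 9 moves from a named harm, to a list of relevant adverse events, to a set of safety outcomes, and anxiety drops out at the last step. Worry is closer to anxiety than to depression. The protocol treats the two as separate constructs with separate scales, and it gives no reason for monitoring only one of them. That both are expected in this population is no such reason, since the remark covers depression equally.

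Because separate AE reporting is waived, the pre-defined list is the only route by which the protocol itself turns questionnaire answers into safety data. A child or parent whose anxiety worsens without meeting one of the six criteria counts as no safety event, either in the running reports to the TMG, TSC and DMC or in the final safety table. Parents are the more exposed group, because five of the six outcomes concern the child only.

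**Working it through.** The protocol states no figure to reproduce. The check sets the relevant parts side by side.

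**Coverage of the safety list (section 9 and Table 6)**

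| Safety outcome | Person | Anxiety measure? |
|---|---|---|
| MFQ 27 or above and a rise of 5 or more | child | no |
| PHQ-9 15 or above and a rise of 5 or more | parent | no |
| Self-harm frequency | child, 11+ | no |
| Hospital admissions due to emotional difficulties | child | no |
| A&E attendances due to emotional difficulties | child | no |
| Deaths | child | no |

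Anxiety: 0 of 6. Symptom-worsening rules: 2 of 6, both for depression. Outcomes that concern the parent: 1 of 6 (PHQ-9).

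**Use of the four symptom scales (Tables 5 and 6)**

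| Scale | Baseline, 6, 12 months | Mean difference (secondary) | Count of worsened individuals (safety) |
|---|---|---|---|
| MFQ | yes | yes | yes |
| PHQ-9 | yes | yes | yes |
| RCADS | yes | yes | no |
| GAD-7 | yes | yes | no |

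**What follows from the stated rules.** The PHQ-9 rule needs a rise of at least 5, so a rise of 4 or less never counts. GAD-7 runs from 0 to 21. A parent could therefore move across the whole GAD-7 scale, with a PHQ-9 rise of 4 or less, and meet no safety criterion. This is a boundary case that shows the rules leave the gap open. It says nothing about how often such a case would occur.

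**Timing.** Section 9.4 collects safety outcomes at 6 and 12 months. The symptom scales can show worsening present at those points. Earlier distress that has resolved is not measured, apart from self-harm, whose items look back over six months, and any admission or A&E visit reported at 6 months. The rationale sentence claims more than that.

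**The case against.** **Section 9.2 is met as written.** It promises that anxiety symptoms will be collected by questionnaire, and they are. It does not promise a threshold count. That is right, so the point is a gap between the named harm and the safety list, and not a contradiction with 9.2.

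**Nobody would see anxiety by arm before the end.** A reader might infer this from the six-item list and from the absence of an interim efficacy analysis (section 13.2.4). The protocol does not support it. Table 4 gives the DMC data by treatment arm for its oversight role without limiting them to the six criteria. Section 16.5 has it advise on the accumulated data under a charter that is not at hand. Section 13.2.4 rules out an interim efficacy analysis, not descriptive tables.

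**A mean hides worsening in a minority, so a count is needed to detect it.** This too is tempting and does not hold up. The protocol gives no standard deviations or correlations, so any test of it rests on assumptions. I assumed a GAD-7 baseline mean of 5, 8 or 11 and SD 5.5; follow-up equal to the mean plus 0.6 times the baseline deviation plus noise of SD 5; scores rounded and kept within range; and 10% of one arm worsening by 5 points. The table gives the chance of a two-sided 5% result for the planned baseline-adjusted mean and for a count (cut-off 10, 12 or 15 plus a rise of 5 or more).

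| Responders per arm | Planned mean | Count |
|---|---|---|
| 363 (60% of 605) | 24–27% | 17–21% |
| 544 (90% of 605) | 33–38% | 23–29% |

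The mean does better in every setting, and both are weak. The case for the count is therefore consistency with the named harm, not sensitivity. Nor do the documents allow an estimate of how many parents with worsening anxiety the PHQ-9 rule would miss.

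**The risk is low and partly covered.** Section 9 likens the risk to that of a questionnaire study. Self-harm, admissions and A&E attendances may catch severe anxiety in the child. The rationale sentence goes on to say only that deterioration may indicate adverse effects, and section 9.4 discloses the 6- and 12-month timing. All of this stands and keeps the point small. None of it covers the parent.

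**Conclusion.** The point holds in a limited form. The protocol names worry or distress as the only plausible harm and lists anxiety symptoms as relevant adverse events, but it does not define worsening anxiety as a safety outcome for child or parent: 0 of 6 outcomes, with two suitable scales already collected at three time points. For parents the list contains depression only.

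The gap is in what the protocol defines as safety data. Collection is complete, mean anxiety is compared by arm at the final analysis, and the DMC may receive anxiety data under its charter. The conclusion rests on the text of sections 9, 9.2 and 9.7 and Tables 5 and 6, and on no assumed value. It is worth correcting because the correction is cheap, and it does not call the safety of the trial into question.

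**What to change.** 1. Add two descriptive safety outcomes to section 9 and Table 6, both at 6 and 12 months: worsening of the RCADS total anxiety score, each rater against their own baseline, and worsening of parent GAD-7. Use the MFQ and PHQ-9 form, a cut-off plus a minimum rise. The protocol gives no values for either scale, so the blinded TMG should set them. Until then, show the DMC the by-arm distribution of change in both scores. No formal comparison is needed, in line with section 13.2.1.

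2. Reword the rationale sentence in section 9 to say that measures of depression and anxiety are already collected and will capture deterioration present at 6 or 12 months.

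Cost: a short amendment and two more rows in the DMC and final safety tables, derived from stored scores for everyone with a baseline and a follow-up value. No new data collection or participant burden. Two limits remain. Non-responders, and parents of 16–17-year-olds who take part alone, have no GAD-7 score. Some counts will arise from ordinary fluctuation where anxiety is common: under the assumptions given above, about 3% to 17% of parents would meet a GAD-7 rule with no harm present, depending on baseline mean and cut-off. The rows should be read by comparing arms, not as absolute counts.

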Throughout the trial the participant will have the opportunity to ask questions about the trial. Any new information that may be relevant to the participant's continued participation, for example changes to the protocol or study procedures which impact on participants, will be provided through updates to the ePIS which will be notified to participants through text and/or email. Where new information becomes available which may affect the participant's decision to continue, participants will be given time to consider and if happy to continue will be re-consented. Re-consent will be documented through electronic signatures obtained in an updated version of the eICF. This will be requested when follow-up data collection is due. Where relevant new information is available, participants will be asked to re-consent prior to completing follow-up questionnaires. The participant's right to withdraw from the trial will remain.

Young people aged 15 at trial entry, who provided assent at entry to the trial and who turn 16 before their 12-month follow-up will be invited to re-consent using the 16-17 years information sheet and a modified version of the consent form at the next scheduled follow-up visit after their 16th birthday. A link to the relevant participant information and the online consent form will be presented before the follow-up questionnaires, and the young person will be offered the option to discuss the information by telephone with the researcher. If the young person does not complete the consent form then the subsequent questionnaires will not be opened for completion, and data for that time-point will be considered lost to follow-up, but the participant will not be withdrawn from the trial. If applicable the questionnaires due at the next follow-up time-point will still be sent to the participant, along with the request to complete the online re-consent form at this time-point if not completed previously.

	Trial name:	STADIA	Protocol version:	4.1	Date:	01-Aug-2022	Page:	24 of 73
1	Written using WPD 3.1 version 2.0 30-Oct-2017. Effective date: 30-Nov-2017. Template Author: [name]							

Table 2. Consent and participation

WHO WAS REFERRED TO CAMHS?	Young person <11	Young person 11-15		Young person 16-17		
WHO IS INITIALLY CONTACTED?		Parent/carer		Depends on contact details provided with the CAMHS referral*		
WHO CONSENTS?	Parent/carer	Parent/carer	Parent/carer	Parent/carer AND Young person	Young person	

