WHO ASSENTS?	None	Young person	None	None	None	
WHO IS THE PRIMARY PARTICIPANT?**	Parent/carer	Parent/carer	Parent/carer	Young person	Young person	
WHO IS INVITED TO COMPLETE THE DAWBA?	Parent/carer	Parent/carer AND Young person	Parent/carer	Parent/carer AND Young person	Young person	
WHO IS INVITED TO COMPLETE RESEARCH QUESTIONNAIRES?	Parent/carer report on young person Parent/carer self- report	Parent/carer report on young person Parent/carer self- report Young person self- report	Parent/carer report on young person Parent/carer self- report	Parent/carer report on young person Parent/carer self- report Young person self- report	Young person self- report	

For all young people aged <16 the initial contact about the study will be with the parent/carer. The involvement of young people aged 11-15 will be at the discretion of the parent/carer.

* For young people aged 16-17 if the young person's contact details are provided on the CAMHS referral the first contact about the study will be with the young person who can choose to nominate a parent/carer to participate in the trial alongside them or participate alone. If the parent/carer's contact details only are available the first contact will be with the parent/carer and the parent/carer will be asked whether the young person can also be contacted but may choose to refuse this. The parent/carer will not be able to participate in the STADIA trial without the involvement or consent of the young person.

** The primary participant is the person who must provide consent as a minimum requirement in order for randomisation to take place. Assent (of young people aged 11-15) and parental consent (for young people aged 16 and 17) may also be sought but is not mandatory and therefore will not be required prior to randomisation.

	Trial name: STADIA	Protocol version: 4.1	Date:	01-Aug-2022	Page:	25 of 73
--	--------------------	-----------------------	-------	-------------	-------	----------

[figure not shown]

Figure 2. Invitation and consent process for young people aged <16

	Trial name:	STADIA	Protocol version:	4.1	Date:	01-Aug-2022	Page:	26 of 73
,	Writton using WDD 2.1 version 2.0.20 Oct 2017 Effective date: 20 Nev 2017 Template Author: [name]							

[figure not shown]

Figure 3. Invitation and consent process for young people aged 16-17

Enrolment and Randomisation

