8.2.6. Follow-up data collection from records

The following data will be collected from CAMHS records for the 18 month period from randomisation. Periodic searches will be completed over the 18 month reporting period.

- CAMHS referrals and outcome including re-referral
- Documented diagnoses*
- Treatments offered and given
- Deaths

	Trial name:	STADIA	Protocol version:	4.1	Date:	01-Aug-2022	Page:	38 of 73
1	Written using WPD 3.1 version 2.0 30-Oct-2017. Effective date: 30-Nov-2017. Template Author: [name]							

*Site researchers will be allowed to review appointment outcome letters that have been sent up to 3-months after the 12-month and 18-month cut-off, to ascertain information relating to a clinician-made diagnosis decision about the presence of an emotional disorder. The letter must specifically reference the appointment/contact where the appointment/contact is within the 12- or 18-month timeframe. The lag between clinic appointments and appointment outcome letters is variable between Trusts and in some instances can take up to 3 months for the letter to be produced, sent to the patient/GP and uploaded to the clinical records.

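### Self-harm, hospital admissions and A&E attendances come only from participant questionnaires, so they are missing for non-responders and for people who stop questionnaires but leave their CAMHS records open

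*Protocol*

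**What the plan says.** **Source of the safety outcomes.** Section 9 defines admissions and A&E attendances as events "due to emotional difficulties as reported in the resource use questionnaire completed at 6- and 12 months post-randomisation". Self-harm is "Frequency of self-harm in children/young people (aged 11+) based on self-report questionnaire completed at 6- and 12-months post-randomisation". Table 6 (section 13.1) repeats these sources. For admissions and A&E the parent reports for under-16s. At 16-17 the young person reports, and so does the parent if taking part. Table 5 restricts the self-harm measure to the child or young person aged 11 and over, with no parent version. Sections 9.2 and 9.3 say that relevant adverse and serious adverse events are gathered through participant questionnaires and need no separate report.

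**Record search.** Section 8.2.6 provides for periodic searches of CAMHS records over 18 months. The list is "CAMHS referrals and outcome including re-referral", documented diagnoses, treatments and deaths. Death is the only safety outcome taken from records.

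**Who may give no questionnaire.** Section 8.4 allows a participant to "Withdraw from trial intervention and follow-up questionnaires but continue to permit trial data collection from records for use in the analysis". Under Table 2, "The involvement of young people aged 11-15 will be at the discretion of the parent/carer". For a young person who entered at 15 and has since turned 16, section 5.4 states: "If the young person does not complete the consent form then the subsequent questionnaires will not be opened for completion".

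**The concern.** The questionnaires replace conventional serious adverse event reporting, so their completeness decides what the Data Monitoring Committee can see. Some participants will return no form while the trial still reads their CAMHS notes. Under section 8.2.6 as written, an inpatient admission or a self-harm episode documented in those notes would not be recorded as a safety event.

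Two consequences follow. First, the counts understate the true number, and probably by more if families in crisis are less likely to return forms. Second, section 9 sends the data by arm to the committee. Participants know their allocation and only one arm receives a DAWBA report (Table 4), so return could differ by arm. Raw counts would then differ for reasons unrelated to harm. Events that were never collected cannot be restored by a later analysis plan, so the matter belongs in the protocol.

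**Working it through.** **1. Sources compared (sections 8.2.6, 9 and Table 6).**

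| Outcome | Questionnaire source | Listed for record search |
|---|---|---|
| Self-harm | Child's own report, 11+, at 6 and 12 months | No |
| Hospital admission | Resource use questionnaire, 6 and 12 months | No |
| A&E attendance | Resource use questionnaire, 6 and 12 months | No |
| Death | None | Yes, to 18 months |

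**2. Who is lost, by outcome.**

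- Non-responders, and those who stop questionnaires but permit record access: all three outcomes.
- Ages 5-10, and 11-15 year olds who do not self-report: self-harm without hospital contact.
- Those who turn 16 and do not re-consent: their own self-harm report, for that time-point only. Table 6 asks about the last 6 months, so a missed 6-month form is not recovered at 12 months.

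**3. Does any stated allowance cover this?** The only missing-data figure in the sample size section is 10%: 544 / 0.9 = 604.4, rounded up to 605 per arm, 1210 in total. It applies to the primary outcome, which comes from records. It says nothing about questionnaire return, for which the protocol gives no figure.

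**4. Size for admissions or A&E (assumed inputs).** Let r be the return, p1 the risk in responders and p0 the risk in non-responders.

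Share missed = (1 - r) p0 / [r p1 + (1 - r) p0]

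With equal risk this reduces to 1 - r. Taking a 5% risk, 1210 x 0.05 = 60.5 participants have an event:

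| Return r | Captured | Missed | Share missed |
|---|---|---|---|
| 80% | 48.4 | 12.1 | 20% |
| 70% | 42.35 | 18.15 | 30% |
| 60% | 36.3 | 24.2 | 40% |

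If non-responders had twice the risk (p1 = 5%, p0 = 10%), then per arm of 605:

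- r = 80%: 24.2 seen of 36.3, 33% missed
- r = 70%: 21.2 seen of 39.3, 46% missed
- r = 60%: 18.2 seen of 42.4, 57% missed

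A single r for both time-points is a simplification; someone who returns one form of two is partly captured.

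**5. Differential return.** With equal true risk of 5% and assumed return of 60% in one arm and 70% in the other, the counts are 605 x 0.05 x 0.60 = 18.15 and 605 x 0.05 x 0.70 = 21.175, a spurious ratio of 0.86. Divided by forms returned (363 and 423.5), both give 5%. Denominators therefore remove this distortion when return is unrelated to risk, but not otherwise.

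**6. Self-harm coverage.** If 20-50% of children give no self-report by design and 60-80% of the rest respond (both assumed), data exist for between 1210 x 0.5 x 0.6 = 363 and 1210 x 0.8 x 0.8 = 774 of 1210 participants.

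**The case against.** The strongest reply is that this is a reasoned choice. Section 9 argues that completing the DAWBA carries risks close to those of a questionnaire study, that distress is the only plausible related harm, and that existing outcome measures will show it. Safety results are descriptive (section 13.2.1), deaths come from records, and the committee can call an emergency meeting. Telephone completion (section 8.2.5), vouchers (section 18.1) and a possible second reporter at 16-17 all reduce the loss. This is a good argument for treating the point as an improvement rather than a serious defect. It does not make incomplete counts complete.

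Several stronger readings are tempting, and the document does not support them:

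- A reader might infer that the re-consent rule also removes admissions and A&E for those turning 16. It closes only the young person's own forms. The parent is the primary participant for a child who entered at 15 and still completes the resource use questionnaire.
- A reader might infer that self-harm at ages 5-10 is wholly unmonitored. Parents report admissions and A&E for all under-16s and complete the MFQ on the child. What has no source is self-harm without hospital contact.
- A reader might take 33-57% as the loss. That range depends on an assumed doubling of risk in non-responders.
- A reader might conclude that no inpatient or crisis care is extracted at all. Table 6 records treatments offered by CAMHS for any reason, and some such care may be entered there, depending on a proforma and data collection guidelines held separately. It would still not count as a safety outcome.

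The objection to the remedy has force. CAMHS notes will not hold every A&E visit or general-hospital admission. Documentation depends on whether the referral was accepted, which the intervention may change, and Table 4 says that record researchers are likely to become unblinded. Record counts can therefore carry their own difference between arms.

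**Conclusion.** The point holds in a limited form. Three pre-defined safety outcomes have a single questionnaire source, while the 18-month record search does not list them, and section 8.4 creates a group whose notes are read but whose events are not recorded. Deaths are unaffected, and parent-reported admissions and A&E remain for under-16s whenever the parent responds.

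The size cannot be derived from the protocol, which gives neither a return rate nor event rates. At an assumed 60-80% return with equal risk, 20-40% of participants with an admission or A&E event are missed; higher risk in non-responders would raise this. The absence of a source for self-harm without hospital contact at ages 5-10 needs no assumption. A record search would recover only what CAMHS notes contain, and nothing for those who also withdraw record consent.

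**What to change.** In section 8.2.6, section 9 and Table 6, add dated fields to the CAMHS record search for:

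1. mental health inpatient admission, as the priority because it depends least on referral acceptance;
2. documented self-harm;
3. crisis or emergency mental health contact.

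Apply them to all participants with record consent whose 18-month search is not complete, and to completed searches where a re-search is feasible.

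Keep the questionnaire counts. Report each source separately by arm with its own denominator: questionnaires returned, by respondent type, and records searched. State that the record counts are supplementary, will not capture all A&E or general-hospital events, and may differ by arm because documentation depends on referral acceptance and extractors may be unblinded. Show referral acceptance by arm beside them as context. Do not stratify the safety comparison by it, because acceptance occurs after randomisation.

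The cost is a minor amendment, a few fields on the paper CRF and some extraction time. It is not free for early recruits: anyone randomised before February 2021 had reached 18 months by the date of this version (1 August 2022), so for them the change may mean reopening notes already searched.
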